### g) Specimen Banking

NA

### h) Data Management and Confidentiality

- *What information will be included in that data or associated with the specimens?* Information collected on CRF's related to this study (i.e., ECG data, diary entries, outcome data based on questionnaires) will be included in the data. Each of the electronic CRF's used in this study is listed in the attached, approved FDA IDE application identified as G150261 under section "eClinicalOS Unique Pages."
- *Where and how data and specimens will be stored.* This information is provided in the attached DoD submission GW140-157, Attachment 8, pages 4 through 6.
- *How long the data will be stored.* Data will be stored for no longer than seven years from study onset.
- *Who will have access to the data?* Data will be available to study team members of the Pain and Fatigue Study Center as well as to the data management team of electroCore listed in the attached DoD submission GW140-157, Attachment 8, page 3. [name] will be doing the statistical analysis of the data set. He will be given a coded data set comprised of the study outcome variables for analysis.
- *Who is responsible for receipt or transmission of the data and specimens?* The study team of the Pain and Fatigue Study Center will be responsible for receipt and transmission of the data.
- *Describe the steps that will be taken to secure the data (e.g., training, authorization of access, password protection, encryption, physical controls, certificates of confidentiality, and separation of identifiers and data) during storage, use, and transmission.* This information is provided in the attached DoD submission GW140-157, Attachment 8, pages 4 through 7.
- *Describe any procedures that will be used for quality control of collected data.* This information is provided in the attached DoD submission GW140-157, Attachment 8, pages 5 through 6.

*Describe the data analysis plan, including any statistical procedures. Provide a power analysis, if applicable (e.g. pilot study).*

*Power analysis:* A power analysis was conducted with G\*Power 3, specifying a standard Type I error ( $\alpha = .05$ ) and desired power of .80. Results indicate that a total sample of 26 would be sufficient. Given a sample of 40, the proposed research should be amply powered to detect a condition difference in pain severity, even allowing for attrition. Therefore, we will target enrollment to obtain data from 40 evaluable subjects.

	Protocol Name:	Vagus Nerve Stimulation: A Non-Invasive Treatment to Improve the health of Gulf Veterans with Gulf War Illness
	Principal Investigator:	[name]
	Primary Contact Name/Contact Info:	[name]: [contact]
	Date Revised:	07/15/2019
	Study Number:	HSM# 16-00097

*Statistical approach to data:* Safety data will be derived from every subject who used either sham or non-sham apparatus for any period of time. Therapeutic efficacy will be evaluated using both intent-to-treat (for all subjects who sign consent with those dropping out recorded as showing no change from baseline) and per protocol (for subjects who completed the 10 weeks of the blinded phase of the trial).

*Blinded study:* Our primary outcome variable will be post-intervention pain severity in the treatment versus sham condition, controlling for pain severity prior to randomization. We will define success for this variable if it decreases by 30% or more over the course of the trial. Five days of VAS data on pain severity will have been collected prior to randomization and during the last week of the 2.5-month stimulation period. For the primary analysis, these will be averaged to create a single pre-intervention and a single post-intervention pain severity score for each person. Post-intervention pain severity will be regressed on pre-intervention pain severity and intervention condition, using an analysis of covariance (ANCOVA) procedure.

A second analysis will use the pre and post measures of pain severity described above, along with pain severity assessments collected a third of the way and two thirds of the way through the 10 week blinded phase of the trial. These four equally spaced assessments over the 10 week study period will form the basis of a repeated measures analysis of variance in order to plot trajectories of pain as a function of treatment condition. We hypothesize a linear decrease in pain from baseline in the nVNS but not in the sham nVNS condition. Other variables (e.g., MIDAS, physical function part of the SF-36, CES-D) will be analyzed using the same general analytic approach; a simple *t*-test will be used to compare PGIC values between the groups at study end. We will define success criteria for PGIC and PF subscale of the SF-36 as scores of 5-7 and 0.5 SD improvement, respectively. Rate of drop out between the two groups while participating in the blinded phase of the trial will be tested for significance by Fisher’s test.

In order to test whether subjects may have become aware of their treatment condition, we will also test for differences by condition in Measure of Certainty data collected at the end of the 2.5 month blinded treatment phase of the study.

*Open label data analysis:*

In addition to the analyses reported above, the open label methodology permits a test across all participants of improvement following 2.5 months of treatment. Regardless of condition, patients’ 2.5-month pain scores, at the end of the open label phase, will be compared to their baseline scores using a dependent samples *t*-test. It is possible that the sham group will show even greater improvement than those in the actually stimulated group had shown at the end of the blinded trial period. Any such increase in improvement would probably reflect a factor related to their knowing they were receiving the effective treatment – i.e., not blinded. Among patients originally in the active treatment condition, we can test for additional improvements beyond 2.5 months using a repeated measures analysis of variance (ANOVA) approach.

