	Protocol Name:	Vagus Nerve Stimulation: A Non-Invasive Treatment to Improve the health of Gulf Veterans with Gulf War Illness
	Principal Investigator:	[name]
	Primary Contact Name/Contact Info:	[name]: [contact]
	Date Revised:	07/15/2019
	Study Number:	HSM# 16-00097

manufacturer in order to obtain the stimulation data, resulting in a 3-4 day delay in retrieving the data, we will not be able to use this criterion to advance subjects to get an actual unit in the open label phase of the study. Therefore, although we will tell subjects they have to deliver at least 70% of all programmed stimuli in order to get an active unit, the only criterion that will be enforced is that they will have had to complete 70% of diary entries, which will be verified by reviewing their diary logs at Encounter #14. This procedure is in place so that veterans who do not perceive benefit from the treatment [i.e. those receiving sham stimulation] will continue to treat themselves per protocol; this is critical for the overall purpose of the study in order to be able to infer that it was the active treatment that produced the therapeutic effect. If subjects did not continue stimulating themselves, we would be unable to determine whether a placebo effect existed or not.

Encounter 7 – Phone Call: Within 7 ( $\pm 4$ ) days after Encounter 6 (Day 0), subject will receive a phone call from study personnel to inquire about any negative effects of stimulation (Adverse Events, AEs) and to check if they are using the diary after each stimulation.

Encounter 8 – Phone Call: Within 23 ( $\pm 4$ ) days after Encounter 6 (Day 0), subject will receive phone call from study personnel to inquire about AEs, check as to use of diary, rating of widespread pain over past 24 hours on a 10-point VAS, and potential desire to reduce medications.

Encounter 9 – Phone Call: Within 46 ( $\pm 4$ ) days after Encounter 6 (Day 0) subject will receive phone call from study personnel to inquire about AEs, check as to use of diary, rating of widespread pain over past 24 hours on a 10-point VAS, and potential desire to reduce medications.

Encounter 10 – Phone Call: Within 63 ( $\pm 4$ ) days after Encounter 6 (Day 0) subject will receive phone call from study personnel to inquire about AEs, check as to use of diary, rating of widespread pain over past 24 hours on a 10-point VAS, and potential desire to reduce medications.

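### The secondary trajectory analysis states a linear hypothesis but specifies neither a linear arm-by-time test nor a rule for participants who miss one of the two single mid-trial pain calls

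*Combined protocol and SAP*

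**What the plan says.** Section 5(h) of the combined protocol and SAP plans two analyses of blinded-phase pain. For the primary ANCOVA, five ratings are taken before randomisation and five in the last treatment week, and "these will be averaged to create a single pre-intervention and a single post-intervention pain severity score for each person". The second analysis takes those two scores "along with pain severity assessments collected a third of the way and two thirds of the way through the 10 week blinded phase". It continues: "These four equally spaced assessments over the 10 week study period will form the basis of a repeated measures analysis of variance", with the purpose given as "in order to plot trajectories of pain as a function of treatment condition". The hypothesis follows: "We hypothesize a linear decrease in pain from baseline in the nVNS but not in the sham nVNS condition".

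The schedule in section 5(f), Blinded Phase of Study, shows what the middle points are: "Encounter 8 – Phone Call: Within 23" and "Encounter 9 – Phone Call: Within 46" days of Encounter 6, each ±4 days, and each collecting one "rating of widespread pain over past 24 hours on a 10-point VAS".

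The only missing-data rule in section 5(h) concerns drop-outs, who are scored as unchanged from baseline under intention to treat. No contrast, arm-by-time term, covariance structure or sphericity correction is named.

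**The concern.** There are three gaps between the method and its purpose.

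- **Test.** A linear difference between arms is a 1-df question. The default group-by-time test of a four-point repeated-measures ANOVA has 3 df and also responds to any other difference in shape. With no contrast named, the choice of test is left open until the data are in.
- **Missed calls.** The classical method needs all four values. A participant who remains in the trial but misses Encounter 8 or 9 has an empty cell that the drop-out rule does not cover. Complete-case handling would exclude that participant while intention to treat keeps a drop-out.
- **Precision and spacing.** Two points average five ratings and two are single ratings, so equal variances of differences are doubtful by design. Spacing is only nominally equal. The last five ratings fall on days 63, 65, 67, 69 and 70 (mean 66.8), and the baseline ratings run back from day 0. The gaps are therefore more than 23, then 23, then 20.8 days, before the ±4-day windows.

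At stake are the power and interpretability of the only planned between-arm comparison of the course of pain, in a trial meant to supply proof-of-principle data for a multi-site proposal.

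**Working it through.** **The plan's own figure.** The documents give no power for the trajectory analysis. Their one figure, N = 26 for the primary ANCOVA (f² = 0.35, α = 0.05, power 0.80), reproduces. With a noncentral F on 1 and N − 3 df and λ = 0.35N, power is 0.807 at N = 25, 0.824 at N = 26 and 0.954 at N = 40. It is not in question here.

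**Assumptions.** The documents give no SDs or miss rates for these ratings. Assumed: 20 per arm (from the planned 40, half per arm); between-person SD 1.5; daily SD σw = 1.5 or 2.0; SD of individual slopes σs = 0 or 1.5 points over the period; linear arm difference reaching 1.5 points at the end; two-sided α = 0.05.

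**Precision of the points.** A single rating has variance 1.5² + σw²; a five-rating mean has 1.5² + σw²/5. For σw = 1.5 this is 4.5 against 2.7. For σw = 2.0 it is 6.25 against 3.05.

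**Complete cases.** If the five-rating means use whatever ratings are available (the plan does not say), only Encounters 8 and 9 can empty a cell. Complete cases are then 40(1 − m)²: 38.4, 36.1, 32.4 and 28.9 for miss rates m of 2%, 5%, 10% and 15% per call.

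**Linear contrast, no missed calls.** L = −3Y₀ − Y₁ + Y₂ + 3Y₃ at times 0, 1/3, 2/3 and 1.

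- Arm difference: 1.5 × (−1/3 + 2/3 + 3) = 1.5 × 10/3 = 5.
- Var(L) = (10/3)²σs² + (9/5 + 1 + 1 + 9/5)σw² = 11.11σs² + 5.6σw².
- SE = √(Var(L) × 2/20). Power comes from a noncentral t on 38 df.

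The 3-df column is simulated without sphericity correction; repeat runs agree within about 2 percentage points.

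| σs | σw | Var(L) | SE | 5/SE | 1-df linear | 3-df omnibus |
|---|---|---|---|---|---|---|
| 0 | 1.5 | 12.6 | 1.12 | 4.45 | 99% | 80% |
| 0 | 2.0 | 22.4 | 1.50 | 3.34 | 90% | 46% |
| 1.5 | 1.5 | 37.6 | 1.94 | 2.58 | 71% | 58% |
| 1.5 | 2.0 | 47.4 | 2.18 | 2.30 | 61% | 38% |

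A Greenhouse–Geisser correction lowers the 3-df range to about 34–71%.

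**Missed calls (σs = σw = 1.5, m = 10%).** About 16.2 per arm are complete. SE = √(37.6 × 2/16.2) = 2.16 and 5/2.16 = 2.3, which gives about 61%. Simulated power:

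| | 3-df omnibus | 1-df contrast, complete cases | Mixed model, all data |
|---|---|---|---|
| None missed | 58% | 73% | 77% |
| 10% of each middle call missed | 45% | 60% | 76% |

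The mixed-model figures treat the covariance as known, so they are slightly optimistic. In this scenario most of the complete-data gap (58% to 73%) comes from testing 1 df instead of 3. The further gain from the mixed model is about 4 points with complete data and about 16 points with missed calls, so it comes mainly from keeping those participants.

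**Type I error.** With no true difference, the uncorrected 3-df test rejects in about 5–7% of simulated trials.

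**The case against.** The strongest reply is that this is a secondary analysis meant for plotting trajectories. The primary ANCOVA uses neither middle call, so the main conclusion cannot change. That stands. So do these points:

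- **A linear contrast can be taken within repeated-measures ANOVA.** A reader might infer that the chosen method cannot address the hypothesis. The documents do not support that: the plan is silent on the contrast, not contrary to it.
- **No exclusion is written down.** A reader might infer that the plan drops anyone who misses a call. It does not say so. Exclusion is a property of the classical method. It arises only for Encounter 8 or 9 if the means use available ratings, and drop-outs are retained by rule.
- **Other outcomes are not affected.** Section 5(h) refers to the same general approach for other variables. But MIDAS and SF-36 are collected only at Encounters 6 and 14 in the blinded phase, so no four-point ANOVA arises for them.
- **The 1.5-point effect is below the design effect.** With σs = σw = 1.5, the residual SD of post given pre is √(4.95 − 2.25²/2.7) = 1.75, and f² = 0.35 means d = 2√0.35 = 1.18, or about 2.1 points. At 2.0 points with none missed, power is about 85% (3-df) against 93% (linear).
- **The omnibus test has a merit.** If the 1.5-point effect is complete by Encounter 8 and then flat, the contrast difference falls to 1.5 × (−1 + 1 + 3) = 4.5. Then 4.5/1.94 = 2.32 and power is about 62%, against about 74% for the omnibus test.

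What the reply does not answer is that a linear hypothesis is stated with no test attached, and that a missed middle call has no rule.

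**Conclusion.** The point holds as a gap in the specification of a secondary analysis, with a better method available at almost no cost. Over the assumed SDs and a 1.5-point linear difference, the default 3-df test has about 38–80% power against about 60–99% for a 1-df linear test. In the scenario with 10% of each middle call missed, the figures are about 45%, 60% and 76% for the omnibus test, the complete-case contrast and the mixed model. Every SD, effect and miss rate is an assumption, and the advantage of the linear test depends on a roughly linear effect, which is what the plan hypothesises. Unequal precision might suggest a serious false-positive problem, but simulated type I error of 5–7% does not bear that out. The main cost is lost power, together with a choice of test left open.

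**What to change.** Replace the repeated-measures ANOVA in section 5(h) with a linear mixed model on all available blinded-phase pain ratings:

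- Enter post-randomisation ratings at their actual day since Encounter 6. Set all pre-randomisation ratings to time zero, with a common baseline mean across arms. Giving Encounters 2–5 negative days would imply arm differences before randomisation.
- Include a patient random intercept and slope. Use individual ratings, or occasion-specific residual variances if the five-rating means are kept.
- Pre-specify the 1-df arm-by-linear-time estimate with its 95% CI as the test.
- State that no participant is excluded for a missed call.
- Because the linear test loses power when an effect is early and then flat, plot visit means by arm and report a model with categorical time (arm-by-visit) as a supportive check.

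The cost is a paragraph of SAP text and slightly more modelling. No new data, visits or participants are needed.

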treatments for these two disorders also treat widespread pain (WSP), we hypothesized that VNS might also impact the same pathophysiological processes and relieve WSP. That hypothesis was initially supported by several papers showing a reduction in pain in patients receiving VNS for treatment of their seizures or for their depression. These data led us to propose a study to determine if VNS would reduce pain and improve the health of patients with treatment-resistant fibromyalgia (FM), a syndrome of WSP with tenderness on palpation. That study, allowing us to assess the safety and tolerability of VNS in FM, was funded by an NIH grant, and is now completed with results published in the medical literature.

In our study of VNS treatment of FM, we used three outcome measures: (1) a 30% improvement from baseline ‘usual pain ratings in the last week’ (at least 5 on a 0 to 10 pain intensity scale was required on intake to participate); (2) Patient Global Impression of Change score rated as markedly or moderately improved (highest two self ratings on a 7 point scale); and (3) an improvement of at least 6 points (0.6 SD) on the Physical Function subscale of the SF-36. Most drug trials in FM use only pain reduction as the major outcome variable. For this study, we required patients to fulfill all three criteria – a very conservative outcome measure.

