#### Secondary:

- Change in the Patient’s Global Impression of Change (PGIC) scale scores of overall symptom burden as completed by the subject from study onset to end of the blinded phase of the trial. Assessment of this endpoint will be based on a comparison between change occurring in active-treated versus sham-treated.
- Change in physical function subscale of the SF-36, a questionnaire assessing health related quality of life from study onset to end of the blinded phase of the trial. Assessment of this endpoint will be based on a comparison between change occurring in active-treated versus sham-treated.
- The difference between the active and sham treatment groups in change in number of migraine/headache days in the final week of the randomized/blinded period from the week prior to randomization.

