#### Others:

- Improvement in the subject’s coexisting disorders as measured by the corresponding scales below, as compared with baseline measures to the blinded period:
  - Migraine: Migraine Disability Assessment Test (MIDAS)
  - Anxiety and Depression: Hospital Anxiety and Depression Scale (HADS)
- Comparison of active versus sham device data as to change in the use of pain or headache medications taken at the end of the randomized/blinded period compared to baseline.
- Adverse events

	Protocol Name:	Vagus Nerve Stimulation: A Non-Invasive Treatment to Improve the health of Gulf Veterans with Gulf War Illness
	Principal Investigator:	[name]
	Primary Contact Name/Contact Info:	[name]: [contact]
	Date Revised:	07/15/2019
	Study Number:	HSM# 16-00097

- A subject's study participation would stop if a patient's symptoms became such that the patient requested stopping or the study doctor felt symptom severity required stopping.

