## f) Procedures Involved in the Human Research

### Source data to be used in Study

*Numerical Rating Scale:* This is a zero to 10 visual analog scale asking veterans to rate the severity of their body-wide pain in the last 24 hrs where zero is no pain and 10 is worst pain possible.

*Kansas Criteria:* These criteria are followed in diagnosing Gulf War Illness. This is done via the history which collects medical information used to diagnose GWI through the endorsement of musculoskeletal pain at moderate or severe intensities. In addition to pain, veterans must endorse symptoms in at least 2 more of the following problem areas: Fatigue/sleep; cognitive and mood; Gastrointestinal; respiratory; skin.

*SF-36:* This is a 36 question vehicle used to assess a patient's health related quality of life. The version for veterans will be used. The physical function subscore will be one of the outcome measures

*Patient Global Assessment of Change:* This scale consists of 7 questions, each scored with a scale ranging from +3 [very much improved] through 0 [no change] to -3 [very much worse]

*Number of migraine days in the past week:* A migraine day is one where a patient has a headache lasting at least 4 hours

*Diary:* Patients will be required to complete a diary after they self administer each treatment to each side of his/her neck. The diary asks the time of the treatment and the stimulus intensity elected by the subject. After the final treatment for that day, the diary asks the patient if s/he has had a headache lasting at least 4 hours.

*Electronic Diary:* Patients will be required to complete a diary after they self administer each treatment to each side of his/her neck. The electronic diary asks the time of the treatment and the stimulus intensity elected by the subject. After the final treatment for the day, the diary asks the patient if s/he has had a headache lasting at least 4 hours. The electronic diary mirrors the paper diary, except that it is online with a secured web address. The subject can access with any electronic device with the capability of accessing the internet. A subject is given a unique 10 digit subject number to access the website. No other information is collected by the subject. Upon logging in for the first time, the subject creates a password and is the only person that can log into their eDiary. This is given as an option for subjects who prefer to use the electronic version over the paper version.

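### The PGIC success cut-off of 5-7 lies outside the +3 to -3 scale described for the trial, and the analysis section names CES-D, which these documents do not schedule, but not HADS, which they do

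*Combined protocol and SAP*

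**What the plan says.** **PGIC.** It is the first-listed secondary endpoint in section 5 e), where it is described as "Global Impression of Change (PGIC) scale scores of overall symptom burden as completed by the subject". Section 5 f), Source data, describes the instrument under a slightly different name (with Assessment in place of Impression): "This scale consists of 7 questions, each scored with a scale ranging from +3 [very much improved] through 0 [no change] to -3", the last value being the worst outcome. Section 5 h), Blinded study, then says: "We will define success criteria for PGIC and PF subscale of the SF-36 as scores of 5-7 and 0.5 SD improvement, respectively". The planned comparison is a t-test that "will be used to compare PGIC values between the groups at study end". For intent-to-treat, the same section keeps dropouts in the analysis, "with those dropping out recorded as showing no change from baseline".

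Section 2) Background reports the PGIC rule used in the team's implanted-device study in fibromyalgia. Success there meant the "highest two self ratings on a 7 point scale".

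**Mood.** Section 5 h) states: "Other variables (e.g., MIDAS, physical function part of the SF-36, CES-D) will be analyzed using the same general analytic approach". Section 5 e), under Others, lists HADS as the measure for anxiety and depression. Section 5 f) describes HADS and schedules it by name at Encounter 6, and again at Encounters 14 and 22 by reference back to the same questionnaires.

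**The concern.** A success rule should be usable on the scale the patient fills in. Here the rule and the scale share no values, and nothing in the documents connects them. Whoever computes a PGIC success rate must choose a coding. If that is done after the data are seen, readers cannot check the reported rate against the plan. The breadth of the rule is also open, because the likely reading differs from the team's own precedent.

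For mood, the one instrument named for analysis is in no endpoint, instrument description or encounter in these documents, while the scheduled instrument is not named. A reader cannot tell which mood result the plan commits to.

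**Working it through.** No stated figure needs reproducing on this point. The check is a comparison of sections plus a short enumeration.

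**1. Which PGIC scores fall in 5-7?** Let x be the item score as described in section 5 f), so x is one of -3, -2, -1, 0, +1, +2, +3.

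| Reading | Score used | Values of x in 5-7 |
|---|---|---|
| As described | x | none (maximum is 3, below 5): 0 of 7 |
| Recode 1-7, 7 best | x + 4 | +1, +2, +3: 3 of 7 |
| Recode 1-7, 1 best | 4 - x | -1, -2, -3: 3 of 7, all worsening |

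The third row can be set aside, because the plan calls 5-7 success. The second row is the likely intent.

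**2. One item or seven?** Section 5 f) says seven questions. The endpoint in section 5 e) is a single rating of overall symptom burden, and the Background speaks of a 7-point scale. The seven questions are therefore probably seven categories of one item, although the text does not say so. Summing seven real questions does not rescue the cut-off: the total would run from 7 × (-3) = -21 to 7 × 3 = +21, and a band of 5 to 7 would reject the better totals of 8 to 21.

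**3. How does the likely reading compare with the precedent?** On a 1-7 scale with 7 best, the highest two ratings are 6 and 7, so x = 6 - 4 = +2 and x = 7 - 4 = +3. The cut-off of 5-7 adds x = 5 - 4 = +1, the mildest grade of improvement. It covers three categories where the fibromyalgia study used two.

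**4. Does the coding affect the t-test?** For a single item, both recodes are linear: y = a + bx with b = +1 or -1. The mean difference is multiplied by b and its standard error by |b|, so |t| does not change and only the sign can. This requires the dropout value to move with the scale: no change is x = 0, which becomes 0 + 4 = 4 on either 1-7 coding. A value of 4 is outside 5-7, so a dropout is not a success under any single-item coding.

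**5. CES-D and HADS, section by section.**

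| Place | CES-D | HADS |
|---|---|---|
| 5 e) Endpoints | absent | listed under Others |
| 5 f) Source data | absent | described, 14 items |
| 5 f) Encounter 1 | not named (PCL5 and PHQ8 are, in an open list) | not named |
| 5 f) Encounter 6 | absent | named |
| 5 f) Encounters 14 and 22 | absent | included by reference |
| 5 h) analysis | named | not named |

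**6. Does this reach the primary analysis?** The ANCOVA uses pain severity before and after treatment plus treatment condition. The sample-size calculation in section 4 uses an effect on pain severity. Neither uses PGIC, CES-D or HADS.

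**The case against.** The strongest reply is that the intent is plain and almost nothing depends on it. A seven-category item coded 1 to 7 with 7 best makes 5-7 a sensible rule. Section 5 f) does give a direction for the scale it describes. No test of PGIC success proportions is planned, and the t-test is the same under any linear coding. HADS falls within the other variables to which section 5 h) applies its general approach, because the named instruments are only examples. CES-D might also be collected: Encounter 1 gives an open list of surveys, and the electronic case report forms are listed in an attachment that is not available here.

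Most of this stands, and it limits the size of the point. It does not supply the missing conversion. The precedent in the Background does not settle the cut-off either, since it used two categories and this rule appears to use three.

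A reader might be tempted to go further in three ways, none of which the documents support:

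- That the plan could count worsening as success. This needs the reverse recode, which the word success makes implausible.
- That HADS has been dropped from the analysis. It is unnamed, not excluded.
- That CES-D is not collected, so the named analysis has no data. The documents show only that CES-D is not in their own endpoints, instruments or encounters.

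**Conclusion.** The text is wrong as written, and the point is minor. The stated PGIC cut-off cannot be met by any item score on the only scale described for this trial, and the named mood variable does not match the scheduled one. The consequence is limited to the PGIC success classification and to which mood measure the plan names.

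This rests on three assumptions. The instrument described in section 5 f) is taken to be the PGIC of the endpoint section, despite the different name. The PGIC is taken to be a single item; if there really are seven questions, the score entering the t-test is also undefined until a combining rule is given. The reading of 5-7 as +1 to +3 is an inference about intent that only the sponsor can confirm.

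A reader might infer that the PGIC comparison as a whole is unsound. For a single item it is not: the t-test result is unchanged. The primary ANCOVA and the sample size are unaffected.

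**What to change.** Before unblinding:

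- In section 5 f) (Source data) and section 5 h) (Blinded study), state that the PGIC is one seven-category item, if that is so. If there are seven questions, state how they are combined.
- Use one coding and direction in both places, and express the success cut-off on that scale. It is +1 to +3 on the described scale if the sponsor confirms that any improvement was intended, given that the fibromyalgia study used only the top two ratings. State the no-change value for dropouts on the same scale.
- Name HADS in section 5 h).
- Check the case report forms for CES-D. If it is not collected, remove it from section 5 h). If it is, add it to the endpoints and the encounter schedule.

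The cost is wording. If the PGIC is a single item, no data, visits or tests change. If there are seven questions, the combining rule would define the score used in the planned t-test. If CES-D is collected, the endpoint and schedule sections need an entry as well.
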